3.3 SAMPLE SIZE CALCULATION/JUSTIFICATION

This multi-center study at up to 8 sites uses a sample size of 6 patients per cohort, yielding 18 total evaluable patients at 3 dose levels. Based on the animal safety studies of SB623, no DLT is expected. However, if the true rate of toxicity is 40%, a sample size of 6 patients per cohort would result in a < 5% chance of missing a DLT.

3.4 STUDY ASSESSMENTS

A table of study assessments can be found in Appendix 10.1.

4. ANALYSIS SETS

4.1 EFFICACY POPULATION

Intent-to-Treat (ITT): The intent-to-treat (ITT) population will include all enrolled patients. Enrolled patients are patients who meet all inclusion/exclusion criteria and qualified for the study or who were granted exceptions to selected inclusion/exclusion criteria, meet all other inclusion/exclusion criteria and qualified for the study, including those who were discontinued from the study or withdrawn for any reason. The ITT population will be used in all efficacy analyses.

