10.0 STUDY ASSESSMENTS

10.1 Schedule of Study Activities

Table 4 below lists the procedures to be followed throughout the course of the study.

Confidential and Proprietary

	Scr. 1	Scr. 2	Baseline ¹	Enroll ²	Cell Admin	Follow-Up Period						Last Eval.	
Study Day			-2 to-1	-1 to 1	1	2	8						
Study Week	-3	-1	1	1	1	1	2						
Study Month								End of 1 and 2	End of 3 and 4	End of 6	End of 9	End of 12	End of 24
Informed Consent	X ³												
Demographics	Х												
Inclusion/Exclusion	Х		Х										
Medical History	Х	X^4	X ⁵	X^6									
Medication History	Х	X^4	X ⁵	X^6									
Signs & Symptoms	Х	X^4	X ⁵	X^6									
Pregnancy Test ⁷	X ⁸		X										
Physical Exam.	Х		Х									Х	Х
Vital Signs	Х	Х	Х				Х	Х	Х	Х	Х	Х	Х
Chest X-Ray and ECG	Х												
Hematology (Section 15.3)	Х	Х	Х				Х	Х	Х	Х	Х	Х	Х
Serum Chemistry (Sect. 15.3)	Х	Х	Х				Х	Х	Х	Х	Х	Х	Х
INR	Х		Х										
Occult Malig. (Sect. 10.2.2)	Х												
Lipid Panel (Section 15.3)			Х				Х	Х	Х	Х	Х	Х	Х
Cytokines (Section 15.3)			Х				Х	X (mo. 2)	X (mo. 4)	Х	Х	Х	Х
Blood for HLA antibodies	X ⁹												
Head CT					Х								
ImagingHead FDG-PET			Х							Х		Х	Х
ImagingHead MRI	X ¹⁰		Х		X ¹¹	Х	Х	X	Х	Х	Х	Х	Х

Table 4 **Study Procedures Flow Chart**

- ⁶ Only changes since Baseline
- ⁷ Only for women of childbearing potential ⁸ Serum β-HCG at Screening; serum or urine β-HCG at Baseline

¹ Only after documentation of stable stroke by two evaluations within 3 weeks prior to study entry using the NIH Stroke Scale (no more than ± 1 point)

² Enrollment only after all inclusion and exclusion criteria are verified and the patient qualifies for the study

³ Prior to any study-related procedures

⁴ Only changes since Screen 1

⁵ Only changes since Screen 2

⁹ May also be done at a pre-Screen visit

¹⁰ May instead be done at a pre-Screen visit ¹¹ Or CT overlaid with MRI from Baseline

	Scr. 1	Scr. 2	Baseline ¹	Enroll ²	Cell Admin	Follow-Up Period							Last Eval.
Study Day			-2 to-1	-1 to 1	1	2	8						
Study Week	-3	-1	1	1	1	1	2						
Study Month								End of 1	End of 3	End	End	End	End
Study Month								and 2	and 4	of 6	of 9	of 12	of 24
Clinical Stroke Evaluations	X ¹²	X ¹²	Х					X	Х	Х	Х	Х	Х
Cognitive Questionnaire			Х							Х		Х	Х
Blood for antibodies to			Х				X	\mathbf{V} (max 2)	\mathbf{V} (ma \mathbf{A})	Х	Х	X	X
SB623 and for PBMCs			Л				Λ	X (mo. 2)	X (mo. 4)	Λ	Λ	Λ	Λ
Serum Antibod. (see Sect.													
15.6 for assay schedule)													
PBMC Function (see Sect.													

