10.3.2 Enrollment (Days -1 or 1)

Enrollment can only occur after performing all assessments and verifying that the patient meets the inclusion and exclusion criteria for the study.

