18.2 Patients to be Included in the Analyses

18.2.1 Efficacy Population

The intent-to-treat (ITT) population will include all enrolled patients, including those who were discontinued from the study or withdrawn for any reason. The Evaluable population will be defined in the Statistical Analysis Plan.

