18.2.2 Safety Population

The safety analyses will include all enrolled patients who have received Study Drug and who have any post-Baseline data.

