19.4 Adherence to the Protocol

The study shall be conducted as described in this protocol except for an emergency situation in which proper care of the patient requires immediate alternative intervention. This protocol refers to the protocol as provided by the Sponsor and approved by both the IRB and the FDA. All of these versions of the protocol must be the same. While FDA regulations permit the protocol to be amended, this must be done in accordance with the provisions agreed upon on Section 19.5. Any deviation from the design of the study as set forth in this document must be recorded as a protocol deviation and be explained in detail as it occurs and/or is detected.

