4.2 SAFETY POPULATION

Safety Population: The safety population will include all enrolled patients who have received treatment with SB623 and who have any post-baseline data. The safety population will be used in all safety analyses.

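### SAP 4.1 ties enrolment to eligibility or a granted exception, so read literally a treated patient who failed a criterion without an exception is outside both the ITT and safety populations

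*SAP*

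**What the plan says.** **Who is enrolled.** SAP 4.1 builds ITT on enrolled patients and then defines the term: "Enrolled patients are patients who meet all inclusion/exclusion criteria and qualified for the study or who were granted exceptions to selected inclusion/exclusion criteria". The second group is, in full, those "who were granted exceptions to selected inclusion/exclusion criteria, meet all other inclusion/exclusion criteria and qualified for the study".

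**Safety population.** SAP 4.2: "The safety population will include all enrolled patients who have received treatment with SB623 and who have any post-baseline data". Protocol 18.2.2 is built the same way: "The safety analyses will include all enrolled patients who have received Study Drug and who have any post-Baseline data".

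**Protocol ITT.** Protocol 18.2.1: "The intent-to-treat (ITT) population will include all enrolled patients, including those who were discontinued from the study or withdrawn for any reason". It mentions no exceptions.

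**Enrolment rule.** Protocol 10.3.2: "Enrollment can only occur after performing all assessments and verifying that the patient meets the inclusion and exclusion criteria for the study". Footnote 2 to Table 4 in Protocol 10.1 repeats it, "Enrollment only after all inclusion and exclusion criteria are verified and the patient qualifies for the study", and SAP Appendix 10.1 carries the same footnote.

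**Departures.** Protocol 19.4 requires the study to be run as written "except for an emergency situation in which proper care of the patient requires immediate alternative intervention", and requires any deviation to be recorded and explained. Protocol 19.5 describes how the investigator contacts the sponsor when a departure is needed. It does not mention eligibility exceptions, and it names changes to eligibility criteria among the substantive changes that need ethics approval.

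**Related SAP text.** SAP 7.1 states that nothing in the protocol-specified analyses has changed. SAP 7.2.3 lets the sponsor decide, before database lock, to leave patients out of the safety and efficacy evaluations because of a deviation.

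**The concern.** The primary objective is safety, so the safety denominator should be fixed by a fact that nobody can revise: receipt of SB623. Here it rests on enrolment, and SAP 4.1 makes enrolment rest on eligibility or on an exception having been granted. A treated patient who failed a criterion could therefore be in or out of the safety tables according to whether an exception is on file. That patient's events are among those that a reader of a first-in-human implant study most needs to see.

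The exception route is a second difficulty. The protocol text to hand does not provide for it. Neither document says who grants an exception, when, or for which criteria. SAP 7.1 nevertheless reports no change from the protocol.

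**Working it through.** **1. The definitions applied to a treated patient with post-baseline data**

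SAP rule: enrolled = (meets all criteria and qualified) or (exception granted, meets all other criteria and qualified). Safety = enrolled and treated and any post-baseline data.

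| Treated patient | Enrolled under SAP 4.1? | ITT | Safety |
|---|---|---|---|
| Meets every criterion | Yes, first limb | In | In |
| Fails one criterion, exception granted for it | Yes, second limb | In | In |
| Fails one criterion, no exception | Neither limb | Out | Out |
| Exception for one criterion, fails another without one | Neither limb | Out | Out |

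The last two rows are the gap. The second row shows the conflict: under Protocol 10.3.2 that patient should not have been enrolled at all.

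**2. What depends on the safety population**

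- Dependent: the analyses in SAP 7.4, and every table numbered 14.3 in SAP 9.2, all labelled Safety. These include treatment-emergent and serious adverse events.
- Not directly dependent: the adverse event and DLT listings in SAP 7.4.1 and 9.3, which carry no population restriction; the stopping rule in Protocol 9.1 and 14.0, which counts patients in a cohort; and the DSMB review in SAP 7.6, which covers all patients in each cohort.

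**3. The plan's own figure**

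Inputs from Protocol 18.5 and SAP 3.3: six patients per cohort, 18 in all, assumed true toxicity rate 40%.

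- P(no DLT among 6) = 0.6^6 = 0.0467. The stated figure of below 5% reproduces.
- If only 5 were counted: 0.6^5 = 0.0778. If only 4: 0.6^4 = 0.1296.

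The plan's figure describes patients dosed and observed, not membership of an analysis set. The values for 5 and 4 would apply only to a summary that counted the reduced set.

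**4. Size if one treated patient were lost (an assumption; the documents give no number)**

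- Share of a cohort: 1/6 = 16.7%. Share of the trial: 1/18 = 5.6%.
- Event in two of six patients, one of them the lost patient: 2/6 = 33% becomes 1/5 = 20%.
- Event never seen, one-sided 95% upper bound 1 − 0.05^(1/n): 15.3% for n = 18 and 16.2% for n = 17.

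The effect is visible in a cohort rate and small in the pooled bound.

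**The case against.** The best defence is that enrolment is a dated step, at Day −1 to 1, taken once eligibility has been verified. A patient who passed that step did qualify, and a later finding does not undo it. On this reading the exception clause only widens ITT, by keeping in patients who might otherwise be dropped. The reading is reasonable and may be what was meant. It does not settle the matter, because SAP 4.1 asks for two things, meeting all criteria and having qualified, and does not say that the first is judged only at enrolment.

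Four other points stand:

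- The protocol is not free of the problem. Its safety set is also tied to enrolment, and its enrolment rule is itself conditional on verified eligibility.
- Protocol 19.4 should not be read as allowing departures for emergencies alone, since 19.4 also covers recorded deviations and 19.5 gives a general departure procedure. Neither mentions eligibility exceptions.
- The SAP and its addendum are based on protocol amendment 4.5, while the protocol supplied is Amendment 5.0. What 4.5 said about exceptions cannot be seen.
- The magnitude is hypothetical, and safety oversight during the trial does not run through the analysis sets.

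A reader might go further and infer that the SAP authorises waivers of protective criteria, or that exceptions could be granted after implantation. The documents support neither. SAP 4.1 names no criterion and gives no timing. A definition of an analysis set says how patients are analysed; it does not permit anyone to be treated.

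**Conclusion.** The concern holds as a defect of definition, of moderate severity. Taken literally, SAP 4.1 and 4.2 place a treated patient who failed a criterion without a covering exception outside both populations, and so outside the safety summaries for the primary objective. The exception route conflicts with Protocol 10.3.2, Table 4 footnote 2 and SAP Appendix 10.1, and those passages must be reconciled.

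The size rests on three assumptions: that such a patient exists, that the literal reading is applied, and that the patient had an event. With one such patient, 16.7% of a cohort is lost and a 33% rate could be shown as 20%.

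It would be wrong to conclude that any patient was in fact excluded, that dose escalation was compromised, or that safety events were hidden from the DSMB. The documents show no such case.

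**What to change.** 1. **SAP 4.2:** define the safety population as all patients who received any SB623, regardless of eligibility. Align Protocol 18.2.2, or record the difference and correct the no-change statement in SAP 7.1.
2. **SAP 4.1:** define ITT by the recorded enrolment event, with no condition on eligibility determined later or on an exception.
3. **Listings 16.2.1 and 16.2.3:** show every unmet criterion and every exception, by patient.
4. **SAP 7.2.3:** state that a protocol deviation cannot remove a treated patient from the safety evaluation. Without this, the discretion remains even after SAP 4.1 and 4.2 are corrected.
5. **Reconcile** the exception wording in SAP 4.1 with the enrolment rule in Protocol 10.3.2, Table 4 footnote 2 and SAP Appendix 10.1, and with the protocol amendment on which the SAP is based.

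A run of the Month 6 ESS analysis without patients who failed a criterion is optional, since SAP 7.1.1 treats all efficacy evaluations as exploratory.

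The cost is a few sentences in the SAP and one matching edit or note for the protocol. It needs no new data and no extra patients.

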4.2 SAFETY POPULATION

Safety Population: The safety population will include all enrolled patients who have received treatment with SB623 and who have any post-baseline data. The safety population will be used in all safety analyses.

5. DEFINITIONS AND DERIVED VARIABLES

Age: Age will be calculated as follows:

[Date of Informed Consent – Date of Birth] / 365.25 rounded down to the nearest integer.

Medical history: Medical history will include significant medical conditions and surgical history, medications taken within 2 weeks prior to signing the Informed Consent, and signs and symptoms occurring within 3 weeks after signing the Informed.

Concomitant medications: Concomitant medication is defined as any medication, including prescription and over-the-counter drugs taken during the 14 days prior to enrollment or used anytime during the study through 2 years post study treatment administration.

Baseline: Baseline will be defined as the last assessment available prior to first infusion of study treatment.

Change from Baseline (CFB): Change will be defined as a given post-baseline value minus the baseline value.

Dose Limiting Toxicity (DLT): A dose-limiting toxicity will be defined as any grade 3 or 4 event which is at least possibly related to study product or administration procedure.

6. ENDPOINTS AND COVARIATES

6.1 **EFFICACY ENDPOINTS**

The primary clinical efficacy endpoint for this study is improvement over baseline of total score and motor function total score using the European Stroke Scale (ESS) at 6 months with all SB623 doses pooled.

Secondary clinical endpoints include (all SB623 doses pooled):

- Improvement of total score, motor function total score, and motor function upper and lower extremity score over baseline using the NIHSS at 6 months of the affected side
- Improvement of scalar assessment over baseline using the MRS at 6 months
- Improvement of total score, motor function total score, and motor function upper and lower extremity score over baseline using the Fugl-Meyer scale at 6 months

Exploratory clinical endpoints include (all SB623 doses pooled):

• Improvement of total score and motor function total score over baseline using the ESS at 1, 2, 3, 4, 9, 12, and 24 months

- Improvement of total score, motor function total score, and motor function upper and lower extremity score over baseline using the NIHSS at 1, 2, 3, 4, 9, 12, and 24 months of the affected side
- Improvement of scalar assessment over baseline using the MRS at 1, 2, 3, 4, 9, 12, and 24 months
- Improvement of total score, motor function total score, and motor function upper and lower extremity score over baseline using the Fugl-Meyer scale at 1, 2, 3, 4, 9, 12, and 24 months
- Improvement in cognitive status using a test battery as described in Table 1 at 6, 12 and 24 months

The exploratory radiographic efficacy endpoints for this study is increase in FDG uptake measured by PET at 6, 12 and 24 months and tissue ratio measured by PET at 6, 12, and 24 months with all SB623 doses pooled.

6.1.1 Description of Clinical Assessment Methods

- European Stroke Scale (ESS): The European Stroke Score is the sum of all 14 parameters. A completely normal person will have a score of 100. The European Stroke Motor Function Score is a sum of the selected parameters: Facial movement, Arm in outstretched position, Arm raising, Extension of wrist, Fingers, leg maintained in position, Leg flexing, Dorsiflexion of foot, and Gait. A completely normal person will have a score of 66. The maximally affected person will have a score of 0 for their total score and motor function total score.
- National Institutes of Health Stroke Scale (NIHSS): The NIHSS is a standardized method used to measure the level of impairment caused by a stroke. The scale consists of 11 items which measures several aspects of brain function, including consciousness, vision, sensation, movement, speech, and language. A certain number of points are given for each impairment uncovered during a focused neurological examination. A maximal score of 42 represents the most severe and devastating stroke with 0 = no stroke, 1-4 = minor stroke, 5-15 = moderate stroke, 15-20 = moderate/severe stroke, and 21-42 = severe stroke. The NIHSS Motor Function Total Score will consist of 3 items: Motor Arm, Motor Leg, and Limb Ataxia and a maximal score of 18 represents the most severe for motor function.
- Modified Rankin Scale (MRS): The MRS is a 1-item Likert scale from 0-5 with 0 representing "No symptoms at all" to 5 representing "Severe disability, bedridden, incontinent requiring constant nursing care, and attention".
- Fugl-Meyer Scale: The Fugl-Meyer Scale is a stroke-specific, performance-based impairment index. It is designed to assess motor functioning, balance, sensation, and joint functioning. The scale is comprised of five domains and there are 155 items in total. Scoring is based on direct observation of performance. Scale items are scored on the basis of ability to complete the item using a 3-point ordinal scale where 0=cannot perform, 1=performs partially, and 2=performs fully. The total possible scale score is 226.

Points are divided among the domains as follows:

• *Motor score:* ranges from 0 (hemiplegia) to 100 points (normal motor performance).

Divided into 66 points for upper extremity and 34 points for the lower extremity. Total motor scores (out of 100 points) are classified based upon the following impairment severity. Total motor scores of <50 = Severe, 50-84 = Marked, 85-94 = Moderate, and 95-99 = Slight.

- Sensation: ranges from 0 to 24 points.
 Divided into 8 points for light touch and 16 points for position sense.
- *Balance:* ranges from 0 to 14 points. Divided into 6 points for sitting and 8 points for standing.
- Joint range of motion: ranges from 0 to 44 points.
- Joint pain: ranges from 0 to 44 points

For purposes of this analysis, the total Fugl-Meyer score, the total of the upper and lower extremity motor score, the total of the upper extremity motor score and the total of the lower extremity motor score will be used. For the motor scores, the total for the upper extremity will be the total of the questions from Sections A-D of the Fugl-Meyer CRF (34 questions with a maximum score of 68 points) and the total for the lower extremity will be the total of the questions E-G of the Fugl-Meyer CRF (27 questions with a maximum score of 54 points).

• Cognitive Battery: Scoring on the tests within the cognitive battery, as detailed in Table 1, are done by the site based upon source documentation provided by the site. Only total score/time/number of correct items are captured on the CRF and entered into the study database. Complete descriptions of the scales and scoring of each test will be described in detail in the clinical study report.

Estimated Intelligence
*Wechsler Abbreviated Scale of Intelligence (WASI) 2 Test
Language
Controlled Oral Word Association Category
Vocabulary (WASI)
Attention
Trails A Time
Digit Vigilance Accuracy
Learning and Memory
Rey Auditory Learning Test
Rey Complex Figure – immediate & delayed recall
Logical Memory – WMS-III
Working Memory
Trails B time and errors

Table 1 – Cognitive Function Test Battery

Letter-Number Sequencing- WMS-III					
Visuospatial/Constructional Ability					
Rey Complex Figure Copy					
Matrix ReasoningWASI					
Psychomotor Efficiency					
Digit Vigilance Time					
Trails A Errors					
Digit Symbol Substitution Test -WAIS-III					
Grooved Pegboard					
Executive Function (reasoning, mental manipulation)					
Stroop Interference					
Controlled Oral Word AssociationFAS					
Mood State and Quality of Life					
Beck Depression Inventory, 2 nd Ed.					
Beck Anxiety Inventory					

* Baseline only

[†] Administered by other study personnel

6.2 SAFETY ENDPOINTS

The safety and tolerability of SB623 cells will be summarized in terms of the following:

- Adverse events (AEs)
- Dose-Limiting Toxicities (DLTs) grade 3 or higher events related to study product or administration procedure
- AEs related to the surgical procedure
- SB623-related AEs
- Serious Adverse Events (SAEs)
- Adverse changes imaged by head magnetic resonance imaging (MRI) (edema, adverse anatomical changes)
- Clinically significant changes in laboratory tests
- Clinically significant changes in physical exam and vital signs
- Development of SB623 serum antibodies
- Changes in PBMC function
- Changes in plasma cytokines

7. STATISTICAL METHODOLOGY AND ANALYSES

This Document is Company Confidential Page 11 of 28

7.1 GENERAL CONSIDERATIONS

Descriptive statistics for continuous variables will include the count of patients (N), mean, standard deviation (SD), median, minimum, maximum and confidence interval (CI, as appropriate); for categorical variables, descriptive statistics will include the number and percentage of patients for each category. Unless otherwise indicated, percentages will be calculated based upon patients with non-missing data as the denominator. When appropriate data will be summarized by dose and visit/time point.

In summary and analysis tables of continuous variables, the minimum and maximum statistics will be presented to the same number of decimal places as the original data. The mean, median, quartiles, and 2-sided 95% confidence interval (CI) will be presented to 1 more decimal place than the original data. The standard deviation and standard error will be presented to 2 more decimal places than the original data.

Analysis of the efficacy endpoints (primary, secondary, and exploratory) will be based on the ITT population defined in Section 4.1. Assessments of tolerability and safety will be based on the safety population defined in Section 4.2.

There are no changes in the protocol-specified analyses.

7.1.1 Hypotheses and Decision Rules

The study is a Phase 1/2A study, with the primary objective of safety and tolerability, and is therefore not powered for multiple efficacy endpoints. All efficacy evaluations are exploratory and no adjustment for multiplicity will be performed. Hypothesis testing of each endpoint will be independently carried out at the 5% (2-sided) significance level.

All statistical analyses will be performed using SAS[®] v9.2 or higher.

